#### **A. Cardiovascular Death**

Cardiovascular death is defined as any of the following contributing conditions:

- Heart failure (sub-classified into left ventricular vs. right ventricular dysfunction)
- Myocardial infarction
- Major bleeding
- Thromboembolism
- Stroke
- Arrhythmia and conduction system disturbance
- Cardiovascular infection and sepsis (e.g., mediastinitis and endocarditis)
- Tamponade
- Sudden, unexpected death
- Other cardiovascular
- Device failure
- Death of unknown cause (adjudicated as cardiovascular)

**B. Non cardiovascular Death**

Any death in which the primary cause of death is clearly related to another condition:

- Non cardiovascular infection and sepsis (e.g., pneumonia)
- Renal failure
- Liver failure
- Cancer
- Trauma
- Homicide
- Suicide
- Other noncardiovascular

**Device Deficiency**

***(ISO 14155:2011 Definition)***

Inadequacy of a medical device with respect to its identity, quality, durability, reliability, safety or performance. This may include malfunctions, use error (outcome of device use was different than intended) and inadequacy in the information supplied by the manufacturer.

**Device Embolization**

***(ISO 5840-3)***

Dislodgement from the intended and documented original position to an unintended and non-therapeutic location

**Device Malfunction**

***(FDA 21 CFR 803.3)***

Failure of a device to meet its performance specifications or otherwise perform as intended. Performance specifications include all claims made in the labeling for the device.

**Device Migration**

***(ISO 5840-3)***

Detectable movement or displacement of the device from its original position within the implant site, without embolization.

**Device Success**

Device is deployed as intended and the delivery system is successfully retrieved as intended at the time of the patient's exit from the cardiac catheterization laboratory. Per device analysis.

Embolism
 
Free flowing blood clot or lesion material that is located in the systemic or pulmonary circulation
 
A peripheral embolic event is an operative, autopsy or clinically documented embolus that produces symptoms from complete or partial obstruction or a peripheral (noncerebral) artery.

Endocarditis
 
An inflammation of the inside lining of the heart chambers and heart valves (endocardium). Endocarditis can involve the heart muscle, heart valves, or lining of the heart.

Enrollment
 
Patient will be considered “provisionally enrolled” when they have signed the informed consent form agreeing to participate in the study and have been deemed eligible for study participation by meeting the study criteria (Sections 7.2-7.3). A patient will be considered “enrolled” at the time of skin incision to introduce the PASCAL System into the body.

Electronic Diary (eDiary)
 
The collection of patient reported outcomes (PRO) through a patient deployed computer or mobile/handheld/tablet device to administer questions/questionnaires to the patient.

Explant
 
Removal of the study device after completion of the implant procedure for any reason.

Heart Failure
 
A progressive condition that involves a supply-demand mismatch, usually due to loss of pumping ability by the heart (heart muscle weakens and gradually loses its ability to pump enough blood through the body), generally accompanied by fluid accumulation in body tissues, especially the lungs and lower limbs.
 
Heart Failure Hospitalization – An unplanned hospitalization that results in at least one overnight stay (i.e., where the admission date and the discharge date are different) that includes increased signs and/or symptoms of worsening heart failure and requires the administration or augmentation of existing heart failure therapy.
 
Severe Heart Failure – See NYHA Class IV

Heart Team
 
The ‘HEART Team’, for the purpose of this study, must include a minimum of one Cardiologist, one Cardiac Surgeon, one Heart Failure specialist, and one Echocardiographer.

**Hemolysis (Device Hemolysis)**

Rupturing of red blood cells (erythrocytes) and the release of their contents (cytoplasm) into surrounding fluids.

Device hemolysis is defined as hemolysis in or near the investigational device that interferes with the function of the device. Device hemolysis related thrombus may be confirmed by operation, autopsy, or diagnostically by such methods as echocardiography, angiography, or magnetic resonance imaging

**Hospitalization/Re-hospitalization**

Hospitalization is defined as any unplanned admission to the hospital (including an emergency department visit) for either a diagnostic or therapeutic purpose following discharge from the index hospitalization.

All hospitalizations will be classified to determine whether the hospitalization was related to:

- **CHF (Congestive Heart Failure) hospitalization:** a hospital stay for  $\geq 24$  hours with signs and/or laboratory evidence of worsening heart failure AND administration of intravenous or mechanical heart failure therapies. An ER stay for  $\geq 24$  hours would qualify as a CHF hospitalization endpoint, even absent formal hospital admission, as such a prolonged stay represents a severe episode of heart failure.
- **Other CV hospitalization:** hospitalization due for coronary artery disease, acute myocardial infarction, hypertension, cardiac arrhythmias, cardiomegaly, pericardial effusion, atherosclerosis, stroke, or peripheral vascular disease without qualifying heart failure.
- **Non-CV hospitalization:** hospitalization that is not due to heart failure or other cardiovascular causes, as defined above

Patients hospitalized with heart failure meeting these criteria should further be subclassified into:

- **Primary (cardiac related) heart failure:** this may be due to any cardiac cause, including primary LV dysfunction with or without medication or dietary noncompliance, acute MI, arrhythmias, and worsening valve dysfunction
- **Secondary (non-cardiac related) heart failure:** when a non-cardiac primary condition is present such as pneumonia, urinary tract infection, or renal failure, which results in fluid overload or myocardial failure.

Note: only primary heart failure should be considered a valid criterion for heart failure hospitalization

**Infection**

Known infection requiring intravenous antibiotics for other than prophylaxis, and/or extended hospitalization.

**Kansas City Cardiomyopathy Questionnaire (KCCQ)**

A health-related quality-of-life measure for patients with congestive heart failure.

**KCCQ-12:** A 12 question abridged and validated version of the full KCCQ questionnaire

**Katz Index of Independence in Activities of Daily Living (Katz ADL)**

Completed by the site, the Katz ADL is a 6 question assessment of functional status as a measurement of the patient's ability to perform activities of daily living

**Major Adverse Event (MAE)**

In this study, MAEs are defined as cardiovascular mortality, MI, stroke, renal complications requiring unplanned dialysis or renal replacement therapy, severe bleeding, unplanned or emergency re-intervention (either percutaneous or surgical) related to the device and major access site and vascular complications requiring intervention.

**Modified Rankin Scale**

- 0: No symptoms at all
- 1: No significant disability despite symptoms; able to carry out all usual duties and activities
- 2: Slight disability; unable to carry out all previous activities, but able to look after own affairs without assistance
- 3: Moderate disability; requiring some help, but able to walk without assistance
- 4: Moderately severe disability; unable to walk without assistance and unable to attend to own bodily needs without assistance
- 5: Severe disability; bedridden, incontinent and requiring constant nursing care and attention
- 6: Dead

**Myocardial Infarction*****(MVARC Definition)***

Myocardial infarction (MI) classification and criteria for diagnosis is defined as follows:

- I. **Periprocedural MI (≤48 hours after index procedure)\*†:**
  - A. **In patients with normal baseline CK-MB (or cTn):**
    - The peak CK-MB measured within 48 h of the procedure rises to ≥10x the local laboratory ULN (Upper Limit of Normal) PLUS new ST-segment elevation or depression of ≥1 mm in ≥2 contiguous leads (measured 80 ms after the J-point)
    - The peak CK-MB measured within 48 h of the procedure rises to ≥5x ULN with new pathological Q waves in ≥2 contiguous leads or new persistent LBBB
    - In the absence of CK-MB measurements and a normal baseline cTn, a cTn (I or T) level measured within 48 h of the PCI rises to ≥70x the local laboratory ULN PLUS new ST-segment elevation or depression of ≥1 mm in ≥2 contiguous leads (measured 80 ms after the J-point)

- The peak CK-MB measured within 48 h of the procedure rises to  $\geq 35$ x ULN with new pathological Q waves in  $\geq 2$  contiguous leads or new persistent LBBB.

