**B. In patients with elevated baseline CK-MB (or cTn):**

- The CK-MB (or cTn) rises by an absolute increment equal to those levels recommended above from the most recent pre-procedure level plus, new ECG changes as described.

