**II. Spontaneous MI (>48 hours after index procedure):**

Detection of rise and/or fall of cardiac biomarkers (preferably cTn) with at least 1 value above the 99th percentile URL (or ULN in the absence of URL) together with at least 1 of the following:

- A. Symptoms of ischemia
- B. ECG changes indicative of new ischemia (new ST-segment or T-wave changes or new LBBB) or new pathological Q waves in  $\geq 2$  contiguous leads
- C. Imaging evidence of a new loss of viable myocardium or new wall motion abnormality

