**III. MI associated with sudden, unexpected cardiac death†:**

Sudden cardiac death or cardiac arrest, often with symptoms suggestive of myocardial ischemia, and accompanied by presumably new ST-segment elevation or new LBBB and/or evidence of fresh thrombus by coronary angiography and/or at autopsy, but death occurs before blood samples could be obtained or at a time before the appearance of cardiac biomarkers in the blood

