**IV. Pathological findings of an acute myocardial infarction‡:**

Note:

The use of high sensitivity (hs)-troponins is recommended for diagnosis of Type II (spontaneous) MI, but has not been studied for assessment of periprocedural MI. Standard troponin assays are therefore recommended for evaluation of Type I MI

Situations where MI is suspected must be carefully evaluated by taking into consideration past medical history, procedural specifics, renal function etc. It is known that cardiac procedures are associated with multiple confounding factors that contribute to myocardial damage

\*Periprocedural biomarker elevation  $>ULN$  not meeting the criteria for MI should be categorized as “myonecrosis not meeting MI criteria.”

†Adapted from Moussa et al.

‡Adapted with permission from Thygesen et al.

New York Heart Association Classification (NYHA Class)
 
Class I: Patients with cardiac disease but without resulting limitations of physical activity.
 
Class II: Patients with cardiac disease resulting in slight limitation of physical activity. Patients are comfortable at rest. Ordinary physical activity results in fatigue, palpitation, dyspnea, or anginal pain.
 
Class III: Patients with cardiac disease resulting in marked limitation of physical activity. Patients are comfortable at rest. Less than ordinary physical activity causes fatigue, palpitation dyspnea, or anginal pain.
 
Class IV: Patients with cardiac disease resulting in inability to carry on any physical activity without discomfort. Symptoms of cardiac insufficiency or of the anginal syndrome may be present even at rest. If any physical activity is undertaken, discomfort is increased

Patient
 
A person with the disease (tricuspid regurgitation) being screened to participate or participating in this clinical study

Patient Preference Survey
 
A survey that includes but is not limited to a patient’s preference for an intervention, clinical outcome/result, or functional change

Peripheral Thromboembolic Event
 
See “Embolism”

Pre-Existing Condition
 
A pre-existing condition is one that was present prior to clinical study screening.

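### Appendix A's fourth periprocedural MI bullet names CK-MB again, so it can decide no case, and I.A is left with no troponin level for new Q waves or LBBB

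*Protocol*

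**What the plan says.** Protocol Appendix A, Myocardial Infarction (MVARC Definition), I.A, covers patients with a normal baseline marker and gives four criteria, each within 48 hours:

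- Bullet 1: CK-MB at least 10 times ULN plus new ST change.
- Bullet 2: CK-MB that "rises to ≥5x ULN with new pathological Q waves in ≥2 contiguous leads or new persistent LBBB".
- Bullet 3: "In the absence of CK-MB measurements and a normal baseline cTn, a cTn (I or T) level measured within 48 h of the PCI", reaching at least 70 times ULN plus new ST change. This is the only troponin criterion.
- Bullet 4: CK-MB of at least "35$ x ULN with new pathological Q waves" or new persistent LBBB.

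I.B, for an elevated baseline, sets no level of its own. It asks that CK-MB or cTn "rises by an absolute increment equal to those levels recommended above", plus the ECG changes described.

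Protocol Tables 4, 7 and 8 let the site draw either troponin or CK/CK-MB by local practice, and Table 11 likewise offers troponin or CK-MB. The note closing the MI entry says: "Standard troponin assays are therefore recommended for evaluation of Type I MI". The contrast there is with high-sensitivity assays, so the note shows that troponin is foreseen, not that CK-MB is discouraged. A footnote says that a periprocedural marker rise "not meeting the criteria for MI should be categorized as" myonecrosis.

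MI is in the MAE list (protocol 5.1 and Appendix A), and clinical success requires freedom from MAEs at 30 days (protocol 5.2.3). SAP 3.1 lists MI without defining it.

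**The concern.** Bullets 1 and 2 form a CK-MB pair: a higher level with ST change, and a lower level with new Q waves or LBBB. Bullet 3 starts what looks like the matching troponin pair, but bullet 4 returns to CK-MB at a level seven times that of bullet 2. The second troponin criterion is therefore absent.

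Troponin-only patients are allowed by the schedule. With up to 30 sites choosing the marker by local habit, a literal reader could class the same event within 48 hours as an MI, and so an MAE and a clinical-success failure, at one site and as myonecrosis at another. Myonecrosis is not in the MAE list. The error would run one way: fewer MIs, a lower MAE rate and, where the procedure succeeded, a higher clinical success rate.

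**Working it through.** The plan states no figure to reproduce here. The check is one of logic, followed by the size of one reclassified patient.

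**Step 1. The four I.A criteria side by side**

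| Bullet | Marker | Level (x ULN) | ECG finding |
|---|---|---|---|
| 1 | CK-MB | ≥10 | ST change |
| 2 | CK-MB | ≥5 | new Q waves or persistent LBBB |
| 3 | cTn, CK-MB absent | ≥70 | ST change |
| 4 | CK-MB | ≥35 | new Q waves or persistent LBBB |

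**Step 2. Can bullet 4 decide a case?**

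- CK-MB measured: a level of at least 35 is also at least 5, with the same ECG finding and window, so bullet 2 is already met.
- CK-MB not measured, or bullet 4 read under bullet 3's condition: bullet 4 cannot be assessed.

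An enumeration agrees. Take CK-MB absent or 0 to 150 x ULN in steps of 0.5 (302 states), cTn absent or 0 to 150 x ULN in steps of 5 (32 states), ST change yes/no and Q waves/LBBB yes/no. That gives 302 × 32 × 4 = 38,656 profiles. Bullet 4 is true in 14,784 and is the only criterion met in 0.

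**Step 3. Troponin-only patients with new Q waves/LBBB and no ST change**

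Of the 31 grid profiles of this kind, 0 are an MI under I.A as printed. If bullet 4 named cTn in the absence of CK-MB (an assumption), the 24 profiles at 35 x ULN or more would be. Patients with both ECG findings and cTn from 35 to below 70 x ULN would also become MIs.

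**Step 4. Evidence in the text that cTn was meant**

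- Bullet 4 follows the bullet for absent CK-MB.
- Its opening repeats that of bullets 1 and 2.
- The levels match as pairs: 70/10 = 7 and 35/5 = 7.

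**Step 5. Size of one patient**

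N = 65 is the protocol's ceiling (12.1), and a smaller denominator makes the step larger. One patient is 1/65 = 1.54 percentage points. The 95% Clopper-Pearson limits (the SAP 6.1 method) are the 2.5% quantile of Beta(x, n−x+1) and the 97.5% quantile of Beta(x+1, n−x):

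- MI line: 1/65 = 1.5% (0.0 to 8.3) becomes 0/65 = 0% (0 to 5.5).
- MAE, with an illustrative count: 4/65 = 6.2% (1.7 to 15.0) becomes 3/65 = 4.6% (1.0 to 12.9).

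**The case against.** The strongest objection is that the operative definition may lie elsewhere. Appendix A says that the CEC Charter will define endpoints further and prevails where the two differ, and protocol 12.4.1 and SAP 8.1 both use adjudicated data. The Charter may already name the right marker. Even if it does not, the slip is easy to see, and the MI note asks for careful evaluation of suspected cases. This stands as a limit on the effect. It does not remove the defect: if the Charter copies Appendix A, there is no inconsistency for it to resolve.

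The affected group is also narrow. A patient needs no CK-MB result, new Q waves or persistent LBBB within 48 hours, a raised troponin that does not meet bullet 3, and no other MAE. The schedule sets minimum tests, and Table 4 adds peri-procedural repeats by local standard of care, so CK-MB might be drawn when an MI is suspected. That stands too.

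A reader might infer that I.B certainly carries the same gap, and that no other MI category could capture such a patient. The text does not settle either:

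- I.B names cTn as an alternative marker for the levels above it, so it can be read as allowing cTn with a Q-wave/LBBB level. It is unclear, not plainly deficient.
- Category II is headed "Spontaneous MI (>48 hours after index procedure", but a marker and an ECG are scheduled at discharge or day 7. Falling troponin with a persisting Q wave after 48 hours might qualify, depending on whether the heading dates the event or its detection.
- Category III is confined to cases where "death occurs before blood samples could be obtained or at a time before the appearance of cardiac biomarkers in the blood", and IV rests on pathological findings. Neither helps a typical survivor.

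**Conclusion.** The wording defect is certain on the printed text: bullet 4 lies wholly inside bullet 2, and I.A states no troponin level for new Q waves or LBBB. The consequence is conditional. If the text is applied literally, each affected patient with no other MAE lowers the MAE rate by 1.54 points at n = 65 and, if the procedure succeeded, raises clinical success by the same amount.

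A reader might infer that the trial's MAE rate will be understated. The documents do not support that. They give no frequency for such patients, who are probably few, and the Charter is not available. The endpoint is summarised without a hypothesis test (protocol 12.4.1), so no error rate or sample size is affected.

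A reader might also take it as settled that cTn was intended. Position and ratios suggest it, but it remains an inference until checked against the source. The point is a small correction to an operative rule of the safety endpoint. It is worth making because it removes classification by local laboratory practice.

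**What to change.** 1. Reconcile bullet 4 of I.A with the MVARC consensus document that the protocol adopts and with the CEC Charter.
2. If the source confirms that troponin was meant, change the marker in bullet 4 to cTn under the condition that CK-MB is absent. This also makes clear what I.B refers back to. In the same edit, time bullet 3 from the index procedure; it now refers to a PCI, which is not the study procedure.
3. Re-check only troponin-only patients with new Q waves or LBBB within 48 hours of the procedure.

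The cost is a small edit to Appendix A in the next amendment, one look at the Charter, and a re-check of a single event type. No analysis method or sample size changes.

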**B. In patients with elevated baseline CK-MB (or cTn):**

- The CK-MB (or cTn) rises by an absolute increment equal to those levels recommended above from the most recent pre-procedure level plus, new ECG changes as described.

**II. Spontaneous MI (>48 hours after index procedure):**

Detection of rise and/or fall of cardiac biomarkers (preferably cTn) with at least 1 value above the 99th percentile URL (or ULN in the absence of URL) together with at least 1 of the following:

- A. Symptoms of ischemia
- B. ECG changes indicative of new ischemia (new ST-segment or T-wave changes or new LBBB) or new pathological Q waves in  $\geq 2$  contiguous leads
- C. Imaging evidence of a new loss of viable myocardium or new wall motion abnormality

**III. MI associated with sudden, unexpected cardiac death†:**

Sudden cardiac death or cardiac arrest, often with symptoms suggestive of myocardial ischemia, and accompanied by presumably new ST-segment elevation or new LBBB and/or evidence of fresh thrombus by coronary angiography and/or at autopsy, but death occurs before blood samples could be obtained or at a time before the appearance of cardiac biomarkers in the blood

**IV. Pathological findings of an acute myocardial infarction‡:**

Note:

The use of high sensitivity (hs)-troponins is recommended for diagnosis of Type II (spontaneous) MI, but has not been studied for assessment of periprocedural MI. Standard troponin assays are therefore recommended for evaluation of Type I MI

Situations where MI is suspected must be carefully evaluated by taking into consideration past medical history, procedural specifics, renal function etc. It is known that cardiac procedures are associated with multiple confounding factors that contribute to myocardial damage

\*Periprocedural biomarker elevation  $>ULN$  not meeting the criteria for MI should be categorized as “myonecrosis not meeting MI criteria.”

†Adapted from Moussa et al.

‡Adapted with permission from Thygesen et al.

New York Heart Association Classification (NYHA Class)
 
Class I: Patients with cardiac disease but without resulting limitations of physical activity.
 
Class II: Patients with cardiac disease resulting in slight limitation of physical activity. Patients are comfortable at rest. Ordinary physical activity results in fatigue, palpitation, dyspnea, or anginal pain.
 
Class III: Patients with cardiac disease resulting in marked limitation of physical activity. Patients are comfortable at rest. Less than ordinary physical activity causes fatigue, palpitation dyspnea, or anginal pain.
 
Class IV: Patients with cardiac disease resulting in inability to carry on any physical activity without discomfort. Symptoms of cardiac insufficiency or of the anginal syndrome may be present even at rest. If any physical activity is undertaken, discomfort is increased

Patient
 
A person with the disease (tricuspid regurgitation) being screened to participate or participating in this clinical study

Patient Preference Survey
 
A survey that includes but is not limited to a patient’s preference for an intervention, clinical outcome/result, or functional change

Peripheral Thromboembolic Event
 
See “Embolism”

Pre-Existing Condition
 
A pre-existing condition is one that was present prior to clinical study screening.


Procedural Success
 
Device success with evidence of a reduction in TR grade by at least one grade (scale: none/trace, mild, moderate, severe, massive, torrential) at end of procedure, and without the need for a surgical or percutaneous intervention prior to hospital discharge. Per patient analysis.

Prosthesis
 
An artificial substitute

Re-intervention (Sponsor Definition)
 
Any intervention on the previously implanted study device (repair, alteration or replacement)

---

Renal Complication (Long-Term)
 
Long-term Renal Complication is defined as onset of renal replacement therapy (i.e hemodialysis, renal transplant)

New need for renal replacement therapy (Sponsor Definition)
 
New need for renal replacement therapy (i.e hemodialysis, renal transplant)

Screen Failure
 
A patient who has signed the consent but, does not fulfill enrollment criteria: does not meet the inclusion criteria or who meets at least one of the exclusion criteria.

Septicemia (Sponsor Definition)
 
Systemic infection requiring hospitalization and treatment with antibiotics.

Serious Adverse Event (SAE) (FDA 21 CFR 812.3)
 
An adverse event that
 
 
• Results in death
 
• Is life-threatening
 
• Requires inpatient hospitalization or prolongation of existing hospitalization
 
• Results in persistent or significant disability/incapacity 
 
○ Is an important medical event which may jeopardize the patient, and may require medical or surgical intervention to prevent one of the above outcomes
 
 
 

Severe Bleeding (Sponsor Definition)
 
Severe bleeding is a fatal, life-threatening, extensive, or major bleeding, as defined by MVARC.

SF-36
 
A survey with 36 questions that results in two scales of mental and physical functioning and overall health related quality of life.
 
SF-12: A 12 question abridged and validated version of the SF-36

**Stroke/TIA (Transient Ischemic Attack)****(MVARC 2015 Definition)****Stroke Diagnostic Criteria:****I. Acute episode of a focal or global neurological deficit with at least one of the following:**

- A. Change in level of consciousness
- B. Hemiplegia, Hemiparesis, Numbness, Sensory loss affecting one side of the body
- C. Dysphasia or aphasia, Hemianopia, Amaurosis fugax, other neurological signs or symptoms consistent with stroke

**II. No other readily identifiable non-stroke cause for the clinical presentation (e.g. brain tumor, trauma, infection, hypoglycemia, peripheral lesion, pharmacological influences) to be determined by or in conjunction with a neurologist.\*****The neurological event type classification****I. Stroke:**

